711 tabulated in a listing of each reported Medical Dictionary for Regulatory Activities (MedDRA)
712 term and summarized over each MedDRA System Organ Class. All enrolled participants will be
713 included in safety analyses.

714 The frequency of each ocular adverse event occurring at least once per eye will be calculated.
715 The proportion of eyes experiencing each outcome will be calculated along with 95% Wilson
716 (Score) confidence intervals. The following ocular adverse events are of primary interest:

- 717 ○ Endophthalmitis
- 718 ○ Retinal detachment
- 719 ○ Retinal tear
- 720 ○ Traumatic cataract
- 721 ○ Cataract extraction in eyes phakic at baseline
- 722 ○ Vitreous hemorrhage
- 723 ○ Adverse IOP events (composite outcome)
 - 724 ■ Increase in IOP ≥ 10 mmHg from baseline (at a follow-up visit)
 - 725 ■ IOP ≥ 30 mmHg (at a follow-up visit)
 - 726 ■ Initiation of medication to lower IOP that was not in use at baseline
 - 727 ■ Glaucoma procedure

728 The frequency of each systemic adverse event occurring at least once per participant will be
729 calculated. The following systemic adverse events are of primary interest:

- 730 ○ Death
- 731 ○ Serious adverse event (at least one)

732 The following systemic adverse events are of secondary interest:

733 ○ For each MedDRA System Organ Class, proportion of participants with at least one
734 serious adverse event

735 In addition, the following will be tabulated:

736 ○ Number of adverse events thought by investigator to be related to treatment

737 **8.9 Intervention Adherence**

738 Adherence will be defined as completion of PVL.

739 **8.10 Protocol Adherence and Retention**

740 Protocol deviations and visit completion rates (excluding deaths) will be tabulated.

741 **8.11 Baseline Descriptive Statistics**

742 Baseline characteristics will be tabulated and summary statistics appropriate to the distribution
743 will be reported.

744 **8.12 Planned Interim Analyses**

745 There is no formal interim analysis planned for this study. The Data and Safety Monitoring
746 Committee (DSMC) will review safety and outcome data approximately every 6 months while
747 the study is ongoing.

748 **8.13 Subgroup Analyses**

749 Subgroup analyses, i.e., assessments of effect modification, will be conducted to detect factors
750 associated with the primary outcome. These analyses will be considered exploratory.

751 Subgroup analyses will be conducted using logistic regression. The relative risk for the subgroup

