Statistical Analysis Plan

DRCR Retina Network Protocol AH: Single-Arm Study Assessing the Effects of Pneumatic Vitreolysis on Macular Hole

ClinicalTrials.gov Identifier: NCT03677869

Version Number	Author	Approver	Effective Date	Revision Description
1.0	[name]	[name]	09 Oct 2019	Initial SAP for Protocol version 2.0
2.0	[name]	[name]	19 Jan 2021	Revisions were made to accommodate a smaller than anticipated sample size after early stopping for safety concerns. Changes were made following review of study data. Details are provided in subsection 1.17. Applies to Protocol version 3.0.

SIGNATURES	
AUTHOR	
APPROVER	

1 **1.0 Overview**

2 The DRCR Retina Network Protocol AH study will evaluate the effectiveness of pneumatic
3 vitreolysis (PVL) in treating eyes with vitreomacular traction (VMT) and full-thickness macular
4 hole (MH). Presence of MH will be graded on optical coherence tomography (OCT) by a reading
5 center prior to enrollment and during follow-up. The primary outcome is at 8 weeks and follow-
6 up continues through 24 weeks.

7 **1.1 Statistical Hypotheses**

8 There are no formal statistical hypotheses that will be evaluated because this is a single-arm
9 study.

10 **1.2 Outcome Measures**

11 For the outcomes below, rescue treatment includes vitrectomy, ocriplasmin, or additional
12 pneumatic vitreolysis during the course of the study.

13 **1.2.1 Primary Efficacy Outcome:**

- 14 • Proportion of eyes with MH closure of the inner retinal layers* without rescue treatment
15 at 8 weeks.
 - 16 ○ For purposes of description only, the distribution of eyes by the following
17 categories at 8 weeks will be tabulated without statistical comparison:
 - 18 ▪ MH closure without rescue treatment
 - 19 ▪ MH closure with rescue treatment
 - 20 ▪ No MH closure and no rescue treatment
 - 21 ▪ No MH closure despite rescue treatment

22 **1.2.2 Secondary Efficacy Outcomes:**

- 23 • Proportion of eyes with MH closure of the inner retinal layers* without rescue treatment
24 through 24 weeks (time-to-event analysis).
- 25 • Proportion of eyes with central VMT release* without rescue treatment through 24 weeks
26 (time-to-event analysis).
 - 27 ○ For purposes of description only, the following will be tabulated without
28 statistical comparison at 8 weeks and 24 weeks:
 - 29 ▪ MH closure with central VMT release without rescue treatment
 - 30 ▪ MH closure without central VMT release without rescue treatment

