1.11 Subgroup Analyses

Subgroup analyses, i.e., assessments of effect modification, will be conducted to detect factors associated with the primary outcome. These analyses will be considered exploratory.

Subgroup analyses will be conducted using logistic regression. The risk difference for the subgroup factor (estimated with conditional standardization),⁴ 95% confidence interval (estimated with the delta method)⁴, and *P* value will be presented. To aid in interpretation of the risk difference, observed outcome proportions will be reported for each subgroup. Subgroup analyses will use data from eyes that complete the 8-week visit or have MH closure or rescue treatment prior to 8 weeks (i.e., complete case analysis as described in section 1.4).

The primary subgroup analysis will evaluate the effect of ERM presence within 1 mm of the center of the macula at baseline.

Secondary subgroup analyses will include ERM presence at the site of vitreous adhesion, lens status (phakic or pseudophakic), retinoschisis, subretinal fluid within 1 mm of the center of the macula, length of adhesion on OCT (less than or equal to 1500 microns or greater than 1500 microns), and diabetes status (has diabetes or does not have diabetes). Subgroups will be defined by the value at baseline.

There are no data to suggest that the treatment success will vary by sex or race/ethnicity. However, both of these factors will be evaluated in exploratory subgroup analyses as mandated by National Institutes of Health (NIH) guidelines.

Subgroup factors will be analyzed as categorical and continuous or ordinal variables where possible. Secondary and exploratory subgroup analyses will only be conducted if there are at

184 least 10 eyes in each subgroup. The primary subgroup analysis will be conducted regardless of
185 sample size.

186 **1.12 Multiple Testing**

187 There will be no adjustments made for multiple testing because this is a single-arm study without
188 treatment group comparisons. Only $P \leq .05$ will be considered of interest.

189 **1.13 Visit Windows for Analysis**

190 The analysis windows for visits will be defined according to Table 1. If multiple visits fall within
191 the same window, priority will be given to the protocol visit over unspecified visits. If there is no
192 protocol visit in the window, then the visit closest to the target date (but within the analysis
193 window) will be designated as the analysis visit. Visit windows will be filled in the following

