194 order to handle visits occurring on the border of two windows: 8 weeks, 24 weeks, 4 weeks, 1
195 week.

196 **Table 1. Analysis Windows**

Visit \pm Protocol Window	Target	Analysis Window
1 week (-4 days to +3 days)	7 days	1 day – 2 weeks (1 – 14 days)
4 (± 1) weeks	28 days	2 – 6 weeks (14 – 42 days)
8 (± 2) weeks	56 days	6 – 18 weeks (42 – 126 days)
24 (± 4) weeks	168 days	18 – 40 weeks (126 – 280 days)

197 **1.14 Missing Data**

198 The strategy for handling missing data generally is included with the description of each
199 analysis. For analyses using multiple imputation, the Markov chain Monte Carlo (MCMC)
200 method with 100 imputations will be used. Where otherwise not specified, only participants with
201 non-missing data will be included in analyses.

202 **1.15 Outliers**

203 To ensure that statistical outliers do not have an undue impact on analyses of continuous
204 outcomes, change in continuous outcomes from baseline will be truncated to ± 3 standard
205 deviations based on the overall mean and standard deviation at 8 weeks. Truncation will occur
206 after imputation, where applicable.

207 **1.16 Model Assumptions.**

208 All model assumptions will be verified. If model assumptions are seriously violated, covariates
209 may be categorized or excluded, and a non-parametric approach, robust method, or
210 transformation may be considered.

211 **1.17 Revisions**

212 Owing to lower than anticipated final sample size, the following key changes were made to the
213 analysis plan after review of study data:

214 • Presence of epiretinal membrane has been removed as a covariate from all imputation
215 and regression models.

216 • Proportion of eyes with central VMT release and vitreopapillary traction (VPT)
217 release without rescue treatment at 24 weeks has been removed from the list of
218 secondary outcomes.

219 In addition, subgroup effects will still be analyzed with logistic regression, but the subgroup
220 effect will be summarized with a risk difference instead of a relative risk.

221 References

222 1. Brown LD, Cai TT, DasGupta A. Interval estimation for a binomial proportion.
223 *Statistical Science*. 2001;16(2):101-117.

224 2. Wilson EB. Probable inference, the law of succession, and statistical inference. *Journal*
225 *of the American Statistical Association*. 1927;22(158):209-212.

226 3. Lott A, Reiter JP. Wilson Confidence Intervals for Binomial Proportions With Multiple

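### After data review the SAP replaced the protocol's relative risk for subgroup factors with a risk difference, without a specific reason and without naming the test behind the P value

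*SAP*

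**What the plan says.** Protocol 8.13 analyses subgroup factors by logistic regression and presents "The relative risk for the subgroup" factor with a 95% interval and P value. This covers the primary subgroup factor (epiretinal membrane, ERM, within 1 mm of the macular center) and the secondary and exploratory factors.

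SAP 1.11 keeps the logistic model but presents "The risk difference for the subgroup factor", obtained by conditional standardization, with a delta-method interval and a P value. SAP 1.17 makes clear that this is a replacement: the "effect will be summarized with a risk difference instead of a relative risk".

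On timing, the SAP version table says of version 2.0: "Changes were made following review of study data". Section 1.17 attributes its bulleted changes to the smaller final sample. The change of measure comes after that list in a separate sentence with no reason of its own.

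SAP 1.12 adds a rule that Protocol 8.14 does not contain: only a P value of .05 or less "will be considered of interest". Secondary and exploratory subgroups need at least 10 eyes each; the ERM analysis runs at any size.

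**The concern.** The protocol's précis names the assessment of factors linked to success as part of the study's purpose. A measure adopted after the data were seen, with the planned one dropped, leaves open whether a factor that stands out would also have stood out as planned. The SAP attaches a P value to the risk difference without saying whether it comes from the delta-method test of that difference or from the logistic coefficient. Section 1.12 then applies a fixed threshold to that P value. At stake is how the ERM result and any other subgroup finding are read, and whether the P value has the error rate that a .05 threshold implies.

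**Working it through.** **The plan's own figure.** The documents give no calculation for subgroups. The only design calculation is Table 1 in Protocol 8.3.2. Its Wilson half-width at 50 eyes and 50% closure is 1.96/(1 + 3.8416/50) × √(0.25/50 + 3.8416/(4 × 2500)) = 1.820 × 0.0734 = 13.4%, as printed. It has no bearing on the subgroup measure.

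**Inputs from the documents.** 50 eyes planned, and fewer enrolled (number not stated); the .05 threshold; a minimum of 10 eyes per subgroup except for ERM.

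**Assumptions.** Splits of 10/25, 12/28 and 15/20, plus 5/25 for ERM. Closure is 35% versus 70%, the reverse, or 60% in both groups.

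**Formulas.** Take a closures in n eyes (smaller group) and b in m (larger group), with p = a/n and q = b/m. With one binary factor the logistic model is saturated, so the delta-method risk difference is the unpooled Wald one.
- Risk difference (RD): p − q, SE = √[p(1−p)/n + q(1−q)/m].
- Relative risk (RR): ln(p/q), SE = √[1/a − 1/n + 1/b − 1/m].
- Likelihood ratio (LR): one-degree-of-freedom deviance test of the factor. It does not depend on the summary measure.

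**One dataset, 3/10 versus 17/25.**
- RD = 0.30 − 0.68 = −0.38; SE = √(0.0210 + 0.0087) = 0.172; interval −0.72 to −0.04; P = .027.
- RR = 0.44; ln = −0.818; SE = √(0.333 − 0.100 + 0.059 − 0.040) = 0.502; interval 0.16 to 1.18; P = .10.
- Odds-ratio Wald P = .049; LR P = .039.

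The RD interval excludes no effect and the RR interval does not. The LR test sides with the RD.

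**All possible datasets.** Every 2×2 table was enumerated exactly. The entries are the percentage of datasets in which the 95% interval excludes no effect, or the LR test gives P below .05. Undefined statistics count as no rejection.

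| Eyes | Closure, smaller / larger | RD | RR | LR | RD and RR differ | RD and LR differ |
|---|---|---|---|---|---|---|
| 10/25 | 35 / 70 | 51.6 | 19.6 | 52.0 | 32.0 | 1.4 |
| 12/28 | 35 / 70 | 58.8 | 28.8 | 57.7 | 30.0 | 1.1 |
| 15/20 | 35 / 70 | 57.8 | 41.6 | 57.5 | 16.2 | 0.3 |
| 10/25 | 70 / 35 | 52.9 | 55.9 | 51.5 | 6.1 | 1.8 |
| 12/28 | 70 / 35 | 59.5 | 59.5 | 56.6 | 0.0 | 2.9 |
| 15/20 | 70 / 35 | 58.6 | 53.2 | 57.4 | 5.4 | 1.2 |
| 10/25 | 60 / 60 | 8.0 | 4.5 | 6.4 | 3.8 | 1.9 |
| 12/28 | 60 / 60 | 7.6 | 4.7 | 5.8 | 2.9 | 1.8 |
| 15/20 | 60 / 60 | 6.7 | 3.7 | 5.9 | 3.0 | 0.8 |
| 5/25 | 60 / 60 | 14.2 | 8.7 | 9.1 | 5.6 | 5.5 |

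**Reading the table.**
- RD and RR part company mainly when the smaller group has the lower closure rate. There the log RR interval has low power, while the RD tracks the LR test closely.
- With 10 or more eyes per group, RD and LR never differ in more than 2.9% of datasets.
- Under no association the delta-method RD test rejects in 6.7-8.0% of datasets at those splits and in 14.2% at 5/25. The LR test rejects in 5.8-6.4% and 9.1%.

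**The case against.** The strongest reply is that the switch changes few verdicts. Judged against a test that does not depend on the measure, the RD is the better behaved of the two when a difference exists, and the large disagreement in one direction comes from the RR interval. That stands. It rules out the tempting inference that the choice of measure by itself decides which factor gets reported.

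SAP 1.17 also says the analysis is still logistic regression and only the summary changes. On a natural reading P then comes from the model and is the same under either measure. That is possible, but the SAP does not say so, and the two candidate P values have different error rates.

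The analyses are labelled exploratory, the change is disclosed, and observed proportions are reported by subgroup. For a binary factor a reader with the counts can compute a crude RR and its interval, so it would be too strong to say readers cannot recover the planned contrast. The proportions do not give the model's RR for factors also analysed as continuous or ordinal.

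There may be a sound reason for the change. The RR is zero or undefined when a subgroup has no closures, which at 30% closure has probability 0.7^10 = 2.8% with 10 eyes and 0.7^5 = 16.8% with 5. The SAP does not offer this reason.

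A reader might also infer that the measure was picked because of the results. The documents do not support that. They show timing and a missing reason, and the version table ties the revision to a smaller sample after early stopping. The RD does not always reject more often either: at 10/25 with the higher rate in the smaller group it is 52.9% against 55.9% for the RR.

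**Conclusion.** The point holds as one of transparency and specification in exploratory analyses. The prespecified relative risk was dropped after data review without a reason specific to that change, and the source of the P value used with the .05 rule is not stated.

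Its size depends on assumed splits and closure rates, because the documents give neither the final number of eyes nor the subgroup sizes. At 10 versus 25 eyes the two intervals differ on excluding no effect in 32% of datasets in the least favorable direction, about 6% in the other, and about 4% with no association. The measures never differ on the null or on direction.

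The more practical matter is the P value. If it is the delta-method one, its error rate is about 7-8% with 10 or more eyes per group and 14% at 5 versus 25. The latter is relevant because the ERM analysis has no minimum size. The primary outcome is unaffected.

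**What to change.** - In SAP 1.11, report the protocol's relative risk with 95% interval beside the risk difference for each factor. Label the first as prespecified and the second as adopted after data review. Mark the relative risk as not estimable where a subgroup has no closures.
- Take the single P value from the likelihood-ratio test of the factor in the logistic model, and apply the rule in 1.12 to that P value only. Its error rate is closer to nominal than the delta-method one but not exact (5.8-6.4% with 10 or more eyes per group, 9.1% at 5 versus 25, under no association at 60%).
- In SAP 1.17, state why the measure was changed.

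The cost is some SAP wording, one extra table column from the same model, and a footnote where the two intervals differ. The reference that the SAP already cites for the risk difference is a paper on relative risks from logistic regression.
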